16.2 Analysis

16.2.1 Treatment emergent AEs

Population: FAS and PPS

Stratification: Table: In the overview table will be presented as treatment i.e. Basaglar and rest by Primary SOC and PT in decreasing order. Listing: By subject

Statistics: Treatment emergent AEs will be listed and summarized as (frequency, percentages) for table.

16.2.2 Drug-related TEAEs

Population: FAS and PPS

Stratification: Table: In the overview table will be presented as treatment i.e. Basaglar and rest by Primary SOC and PT in decreasing order. Listing: By subject

Statistics: Drug-related TEAEs will be listed and summarized as (frequency, percentages) for table.

16.2.3 Serious TEAEs

| Population: | FAS and PPS | |
|-----------------|--|--|
| Stratification: | Table: In the overview table will be presented as treatment i.e. | |
| | Basaglar and rest by Primary SOC and PT in decreasing order. | |
| | Listing: By subject | |
| Statistics: | Serious TEAEs will be listed and summarized as (frequency, | |
| | percentages) for table. | |

16.2.4 Drug related Serious TEAEs

- Population: FAS and PPS
- Stratification: Table: In the overview table will be presented by treatment i.e. Basaglar and rest by Primary SOC and PT in decreasing order. Listing: By subject
- Statistics: Drug related Serious TEAEs will be listed and summarized as (frequency, percentages) for table.

16.2.5 TEAEs by severity

| Population: | FAS and PPS |
|-------------|-------------|
|-------------|-------------|

- Stratification:Table: In the overview table will be presented by treatment i.e.Basaglar and rest by Primary SOC and PT in decreasing order.Listing: By subject
- Statistics: TEAEs by severity will be listed and summarized as (frequency, percentages) for table.

16.2.6 TEAEs leading to death

- Population: FAS and PPS
- Stratification: Table: In the overview table will be presented by treatment i.e. Basaglar and rest by Primary SOC and PT in decreasing order. Listing: By subject
- Statistics: TEAEs leading to death will be listed and summarized as (frequency, percentages) for table.

Page 44 of 85

16.2.7 Drug-related TEAEs leading to death

| Population: | FAS and I | PPS |
|-------------|-----------|-----|
|-------------|-----------|-----|

Stratification: Table: In the overview table will be presented by treatment i.e. Basaglar and rest by Primary SOC and PT in decreasing order. Listing: By subject

Statistics: Drug-related TEAEs leading to death will be listed and summarized as (frequency, percentages) for table.

16.2.8 TEAEs leading to early withdrawal from study

Population: FAS and PPS

Stratification: Table: In the overview table will be presented by treatment i.e. Basaglar and rest by Primary SOC and PT in decreasing order. Listing: By subject

Statistics: TEAEs leading to early withdrawal from study will be summarized as (frequency, percentages) for table.

16.2.9 Serious AEs

Population: FAS and PPS

Stratification:Table: In the overview table will be presented by treatment i.e.Basaglar and rest by Primary SOC and PT in decreasing order.Listing: By subject

Statistics: Serious AEs will be listed and summarized as (frequency, percentages) for table.

16.2.10 Serious TEAEs by severity (Grade 3-5)

Population: FAS and PPS

Stratification: Table: In the overview table will be presented by treatment i.e. Basaglar and rest by Primary SOC and PT in decreasing order. Listing: By subject

Statistics: Serious TEAEs by severity (Grade 3-5) will be listed and summarized as (frequency, percentages) for table.

Page 45 of 85

17. Safety laboratory tests

17.1 Variables and derivations

For safety laboratory data, baseline will be defined as the last observation made prior to the first administration of IMP (see section 7.2).

The following Clinical Laboratory Tests (haematology, clinical chemistry and urinalysis measured at Visit 1, 5 and 8) to be included in the analysis:

- Haematology:
 - o Hemoglobin
 - o Hematocrit
 - Erythrocyte count (RBC)
 - o Mean cell volume
 - Mean cell hemoglobin concentration
 - Leukocytes (WBC)
 - o Neutrophils, segmented
 - o Lymphocytes
 - Monocytes
 - o Eosinophils
 - o Basophils
 - o Platelets
- Clinical Chemistry:
 - o Specific gravity
 - o pH
 - o Protein
 - o Glucose
 - o Ketones
 - o Blood
 - o Urine leukocyte esterase
- Urinalysis:
 - o Sodium
 - o Potassium
 - Total bilirubin
 - o Direct bilirubin

- Alkaline phosphatase
- Alanine aminotransferase (ALT)
- Aspartate aminotransferase (AST)
- Blood urea nitrogen (BUN)
- o Creatinine
- o Uric acid
- o Calcium
- Fasting blood glucose
- o Albumin
- o Cholesterol
- Creatine kinase (CK)

The following Hepatic Monitoring Tests (Hepatic Haematology, Hepatic Chemistry, Hepatic Coagulation and Hepatic Serologies measured at Visit 3, 4, 5 and 8) to be included in the analysis:

- Hepatic Haematology
 - o Haemoglobin
 - o Haematocrit
 - o RBC
 - o WBC
 - Neutrophils (segmented)
 - o Lymphocytes
 - Monocytes
 - o Eosinophils
 - o Basophils
 - Platelets result
- Hepatic Chemistry
 - Total bilirubin result
 - o Direct bilirubin result
 - o Alkaline phosphatase result
 - Alanine Aminotransferase (ALT) result
 - Aspartate Aminotransferase (AST) result
 - o Gamma-Glutamyl Transferase (GGT) result
 - Creatine phosphokinase (CPK) result

- Haptoglobin result
- Hepatic Coagulation
 - Prothrombin time result
 - Prothrombin time, INR result
- Hepatic Serologies
 - Hepatitis A antibody, total result
 - Hepatitis A antibody, IgM result
 - Hepatitis B surface antigen result
 - Hepatitis B surface antibody result
 - o Hepatitis B core antibody result
 - o Hepatitis C antibody result
 - Hepatitis E antibody, IgG result
 - o Hepatitis E antibody, IgM result
 - o Anti-nuclear antibody result
 - Alkaline Phosphatase Isoenzymes result
 - Anti-smooth muscle antibody (or anti-actin antibody) result

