### 10.3.2.2. Laboratory Measurements

Continuous chemistry and hematology measures will be summarized by descriptive statistics at screening visit (Week -2) and at different visits (Section 2) for the FAS population.

Continuous chemistry and hematology measures will be summarized as change from screening visit (Week -2) to Week 24 using the general linear model, with the screening visit (Week -2) value of the response variable as covariate.

All laboratory measurements analyses will be repeated for the PPS population.

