**Clinical Chemistrya,b,c**

**Serum Concentrations of:**  
Sodium  
Potassium  
Total bilirubin  
Direct bilirubin  
Alkaline phosphatase  
Alanine aminotransferase (ALT)  
Aspartate aminotransferase (AST)  
Blood urea nitrogen (BUN)  
Creatinine  
Uric acid  
Calcium  
Fasting blood glucose  
Albumin  
Cholesterol  
Creatine kinase (CK)

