17.2 Analysis

Population: FAS and PPS

Stratification: Table: By visit

Listing: By subject, visit and each laboratory test parameter

Statistics: Summaries of all the clinical laboratory tests (haematology, clinical chemistry and urinalysis) will include descriptive statistics of the following:

- Actual and change from baseline (n, mean, standard deviation, standard error median, minimum, maximum) (for quantitative measurements)
- Frequencies and percentages (n and %) (for qualitative measurements)

Continuous clinical laboratory chemistry and haematology measures will be summarized as change from screening visit (Week -2) to Week 24 using the general linear model, with the change from

week -2 to week 24 in respective laboratory parameter as dependent variable and the screening visit (Week -2) value of the respective response variable as covariate.

Missing data imputation will be performed as mentioned in section 8.2 point 5.

Efficacy tables will be presented for with and without imputed values separately for each population set.

The estimate, 95% confidence interval and p-value will be summarised for efficacy table.

The regression line for the general linear model without categorical variable is as follows:

 $Y = \alpha + \beta (X)$

Where,

Y= The response change in respective laboratory parameter.

 $\alpha = Intercept$

β =slope

X= Covariate i.e. Baseline (i.e. week -2) respective laboratory parameter

The hypothesis is as follows

H0: $\beta = 0$

i.e. There is no statistically significant change in respective laboratory parameter at week 24 from screening visit (Week -2) depending on the Baseline (i.e. week -2) respective laboratory parameter.

V/s

H1: β ≠ 0

i.e. There is statistically significant change in respective laboratory parameter at week 24 from screening visit (Week -2) depending on the Baseline (i.e. week -2) respective laboratory parameter.

The above hypothesis will be tested based on α (alpha)=0.05, if the p-value \geq 0.05 then we will conclude that there is no statistically significant change in respective laboratory parameter at week 24 from screening visit (Week -2) i.e. Ho is accepted.

Page 49 of 85

The sample SAS programme is as follows:

proc mixed data=dataset;

model Y= X / s cl;

estimate "Model with Mean baseline lab parameter" int 1 lab parameter baseline mean /CL;

ods output estimates=output dataset;

run;

quit;

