Quantitative all the clinical laboratory tests (haematology, clinical chemistry and urinalysis) will be compared with the relevant laboratory reference ranges and categorised as:

- Low: Below the lower limit of the laboratory reference range
- Normal: Within the laboratory reference range (upper and lower limit included)
- High: Above the upper limit of the laboratory reference range

i.e. Shift tables (low, normal, high) will be presented for all parameters by treatment and visit.

Data for all the clinical laboratory tests (haematology, clinical chemistry) will also be presented graphically as a function of time. These will include line plots of mean ± standard deviation and median ± range of individual participant's data by treatment and visit.

Note: if we get continuous laboratory test results as < or > value then worst-case scenario will be considered (i.e. for ex. if parameter values are < 40 then it will be considered as 40).

All the hepatic monitoring tests (Hepatic Haematology, Hepatic Chemistry, Hepatic Coagulation and Hepatic Serologies) will be summarised as n, mean, standard deviation, standard error median, minimum, maximum for quantitative measurements also frequencies and percentages (n and %) for qualitative measurements.

All the clinical laboratory tests and hepatic monitoring tests will be listed by subject, visit and each laboratory test parameter.

Note: This Hepatic test present on the case that the patient suffers from hepatic event.

18. Vital signs

The vital sings will be measured on scheduled visits i.e. visit 1 through visit 9 (EOS) except Visit 6 and 7 (telephonic visits).

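### SAP 17.1 exchanges the clinical chemistry and urinalysis lists, so a literal reading leaves the 15 serum analytes without the Week 24 change model and the plots

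*SAP*

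**What the plan says.** Protocol Appendix 2 defines three panels: 12 haematology tests, 7 urinalysis tests, and 15 clinical chemistry tests, the last introduced by "Serum Concentrations of". SAP 17.1 repeats the same tests for analysis, but its Clinical Chemistry list ends with "Urine leukocyte esterase" and its Urinalysis list runs from sodium to creatine kinase.

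SAP 17.2 then assigns analyses by panel name:

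- Descriptive statistics cover all three panels: "Summaries of all the clinical laboratory tests (haematology, clinical chemistry and urinalysis) will include descriptive statistics of the following".
- The model covers two: "Continuous clinical laboratory chemistry and haematology measures will be summarized as change from screening visit (Week -2) to Week 24 using the general linear model".
- The plots cover the same two: "Data for all the clinical laboratory tests (haematology, clinical chemistry) will also be presented graphically as a function of time".

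Protocol 10.3.2.2 has the matching requirement for the model: "Continuous chemistry and hematology measures will be summarized as change from screening visit (Week -2) to Week 24 using the general linear model". It does not ask for plots.

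**The concern.** In most plans a wrong panel heading would be a matter of table titles. Here two analyses are limited by panel name, so the lists in 17.1 determine which tests those analyses cover. A programmer who takes panel membership from 17.1 would leave ALT, AST, bilirubin, creatinine, potassium and the other serum analytes out of the model that the protocol requires. Any urine test reported as a number would go in instead.

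The labels matter too, because several names do not show which fluid was tested. Glucose and protein under Clinical Chemistry can be taken for serum results. Sodium, potassium, creatinine, uric acid and albumin under Urinalysis can be taken for urine results.

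**Working it through.** **1. Compare the panels, test by test.**

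| Panel heading | Protocol Appendix 2 | SAP 17.1 |
|---|---|---|
| Haematology | 12 blood-count tests | the same 12 |
| Clinical Chemistry | 15 serum analytes, sodium to creatine kinase | 7 urine tests, specific gravity to urine leukocyte esterase |
| Urinalysis | 7 urine tests | 15 serum analytes |

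The SAP's Clinical Chemistry list equals the protocol's Urinalysis list (7 of 7, same order). Its Urinalysis list equals the protocol's Clinical Chemistry list (15 of 15, same order). No test in either list is under its protocol heading, so the exchange is complete. It does not look like a fault in reading the PDF: each SAP heading is followed by its own full bulleted list, and the serum list continues across a page break.

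**2. Trace which outputs depend on the panel name.**

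| Output in SAP 17.2 | Panels named | Effect on the 15 serum analytes, read literally |
|---|---|---|
| Actual values and change from baseline, descriptive | all three | kept, wrong heading |
| Low/normal/high shift tables | all three | kept, wrong heading |
| Listings | all | kept |
| General linear model, Week -2 to Week 24 | chemistry, haematology | omitted |
| Plots over time | haematology, clinical chemistry | omitted |

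**3. Count what is affected.**

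- Tests intended for the model and plots: 12 + 15 = 27.
- Tests under those headings as the SAP is written: 12 + 7 = 19. The model takes only continuous measures, so fewer than 19 would enter it. The documents do not say which urine tests are numeric; if only specific gravity and pH are, the model would take 12 + 2 = 14.
- Serum analytes among the 27: 15/27 = 56%.
- SAP 17.2 presents the model for FAS and PPS, with and without imputed values, so the omitted fits number 15 × 2 × 2 = 60 of 27 × 2 × 2 = 108.

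The 56% assumes that all 15 analytes are measured at Week 24. Footnote c of Appendix 2 mentions an abbreviated chemistry of 5 tests (total bilirubin, direct bilirubin, ALT, BUN, creatinine) and refers to the schedule, which does not say when it applies. If it applied at Week 24, the share would be 5/(12 + 5) = 29%. The range is therefore 29% to 56%.

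**4. Ask what the omitted model would have added.** The model is Y = α + βX, with Y the change and X the Week -2 value, and the SAP's sample code estimates it at the mean baseline. Least squares gives α̂ = ȳ − β̂x̄, so the estimate at x̄ is α̂ + β̂x̄ = ȳ. For the same subjects this is the raw mean change. Scheduled laboratory samples before treatment are taken only at Visit 1, so for them the SAP's baseline and the Week -2 value coincide, and ȳ is already in the descriptive table with its SD and SE. What the model adds is an interval based on residual variation after adjusting for baseline, a p-value, and a version with LOCF. The SAP states its hypothesis as β = 0, so that p-value concerns the slope on baseline rather than the change itself.

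**The case against.** The strongest reply is that the documents already contain the correct classification. The SAP's schedule of events refers the reader to protocol Appendix 2 for the laboratory tests, the SAP says that it is based on that protocol version, and a urine test under a chemistry heading is visibly wrong. No passage says that programs take panel membership from 17.1. This stands in part: the error is likely to be caught. But 17.1 states which tests enter the analysis under each heading, and someone who catches the error must then depart from the SAP text to meet the protocol.

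The second reply is that little is lost, and step 4 bears that out: the mean change, its SE, the shift tables and the listings all survive. The plots and the LOCF version are SAP additions, so their absence breaches no protocol requirement.

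Third, laboratory change is not among the endpoints in protocol Table ABEX.2. Clinically significant laboratory findings that lead to a diagnosis are reported as adverse events under protocol 9.4.3, and hepatic monitoring under 9.4.6.1 works from the results themselves. Neither depends on the SAP's headings. This stands.

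The separate hepatic panel does not fill the gap. It repeats total and direct bilirubin, ALP, ALT, AST and creatine (phospho)kinase, but it applies only to subjects with a hepatic event, and it is summarised and listed, not modelled. Nor does the fasting glucose model in SAP 20.2.6, which uses the glucometer reading before breakfast.

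**Conclusion.** SAP 17.1 is wrong as written: all 7 urine tests and all 15 serum analytes stand under each other's heading. Read literally with 17.2, 0 of 15 serum analytes receive the Week 24 model required by protocol 10.3.2.2, or the plots. The severity is minor. The loss is the baseline-adjusted estimate with its interval and p-value (both with and without LOCF), the plots and the correct labels. It occurs only if the programmer follows the 17.1 headings.

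A reader might infer three stronger things that the documents do not support:

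- That the serum changes go unreported. Descriptive change statistics, shift tables and listings cover every panel.
- That the model and plots would run on urine tests alone. The 12 haematology tests are correctly listed and stay in both, and few urine tests are likely to be continuous.
- That safety surveillance is weakened. Adverse event reporting and hepatic monitoring do not use these lists.

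Modelling numeric urine tests is also not plainly contrary to the protocol. Section 10.3.2.2 names only chemistry and haematology, but the synopsis speaks more broadly of continuous laboratory measures. Both require the serum model.

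**What to change.** In SAP 17.1, exchange the two lists so that they match protocol Appendix 2: sodium to creatine kinase under Clinical Chemistry, and specific gravity to urine leukocyte esterase under Urinalysis. The model and plot sentences in 17.2 can then stay as they are and cover the intended 12 + 15 = 27 tests, with urinalysis keeping its descriptive tables, shift tables and listings.

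This is a wording correction to the SAP, best made before programming. It needs no new data and no protocol amendment. The SAP's revision history shows only the initial version, so the correction should be recorded there.

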17.2 Analysis

Population: FAS and PPS

Stratification: Table: By visit

Listing: By subject, visit and each laboratory test parameter

Statistics: Summaries of all the clinical laboratory tests (haematology, clinical chemistry and urinalysis) will include descriptive statistics of the following:

- Actual and change from baseline (n, mean, standard deviation, standard error median, minimum, maximum) (for quantitative measurements)
- Frequencies and percentages (n and %) (for qualitative measurements)

Continuous clinical laboratory chemistry and haematology measures will be summarized as change from screening visit (Week -2) to Week 24 using the general linear model, with the change from

week -2 to week 24 in respective laboratory parameter as dependent variable and the screening visit (Week -2) value of the respective response variable as covariate.

Missing data imputation will be performed as mentioned in section 8.2 point 5.

Efficacy tables will be presented for with and without imputed values separately for each population set.

The estimate, 95% confidence interval and p-value will be summarised for efficacy table.

The regression line for the general linear model without categorical variable is as follows:

 $Y = \alpha + \beta (X)$

Where,

Y= The response change in respective laboratory parameter.

 $\alpha = Intercept$

β =slope

X= Covariate i.e. Baseline (i.e. week -2) respective laboratory parameter

The hypothesis is as follows

H0: $\beta = 0$

i.e. There is no statistically significant change in respective laboratory parameter at week 24 from screening visit (Week -2) depending on the Baseline (i.e. week -2) respective laboratory parameter.

V/s

H1: β ≠ 0

i.e. There is statistically significant change in respective laboratory parameter at week 24 from screening visit (Week -2) depending on the Baseline (i.e. week -2) respective laboratory parameter.

The above hypothesis will be tested based on α (alpha)=0.05, if the p-value \geq 0.05 then we will conclude that there is no statistically significant change in respective laboratory parameter at week 24 from screening visit (Week -2) i.e. Ho is accepted.

Page 49 of 85

The sample SAS programme is as follows:

proc mixed data=dataset;

model Y= X / s cl;

estimate "Model with Mean baseline lab parameter" int 1 lab parameter baseline mean /CL;

ods output estimates=output dataset;

run;

quit;

Quantitative all the clinical laboratory tests (haematology, clinical chemistry and urinalysis) will be compared with the relevant laboratory reference ranges and categorised as:

- Low: Below the lower limit of the laboratory reference range
- Normal: Within the laboratory reference range (upper and lower limit included)
- High: Above the upper limit of the laboratory reference range

i.e. Shift tables (low, normal, high) will be presented for all parameters by treatment and visit.

Data for all the clinical laboratory tests (haematology, clinical chemistry) will also be presented graphically as a function of time. These will include line plots of mean ± standard deviation and median ± range of individual participant's data by treatment and visit.

Note: if we get continuous laboratory test results as < or > value then worst-case scenario will be considered (i.e. for ex. if parameter values are < 40 then it will be considered as 40).

All the hepatic monitoring tests (Hepatic Haematology, Hepatic Chemistry, Hepatic Coagulation and Hepatic Serologies) will be summarised as n, mean, standard deviation, standard error median, minimum, maximum for quantitative measurements also frequencies and percentages (n and %) for qualitative measurements.

All the clinical laboratory tests and hepatic monitoring tests will be listed by subject, visit and each laboratory test parameter.

Note: This Hepatic test present on the case that the patient suffers from hepatic event.

18. Vital signs

The vital sings will be measured on scheduled visits i.e. visit 1 through visit 9 (EOS) except Visit 6 and 7 (telephonic visits).

18.1 Variables and derivations

For vital signs, baseline is defined as the last observation made prior to the first administration of IMP (See the section 7.2).

The following vital signs will be reported for this study:

- Systolic blood pressure (mmHg)
- Diastolic blood pressure (mmHg)
- Pulse rate (beats per minute)

18.2 Analysis

| Population: | FAS and PPS |
|-----------------|---------------------|
| Stratification: | Table: By visit |
| | Listing: By subject |

Statistics: Descriptive statistics (n, mean, standard deviation, standard error, median, minimum, maximum) will be calculated for all the vital signs variables (Actual and change from baseline) for table. Listing will be presented for all the vital signs parameter by subject.

> The change from baseline values to Week 24 will be analysed using the general linear model, with the baseline value of the response variable as covariate after applying the LOCF method to missing values.

> Missing data imputation will be performed as mentioned in section 8.2 point 1.

Efficacy tables will be presented for with and without imputed values separately for each population.

The estimate, 95% confidence interval and p-value will be summarised for efficacy table.

The regression line for the general linear model without categorical variable is as follows:

 $Y = \alpha + \beta (X)$

Where,

Y= The response change in respective vital signs parameter.

 $\alpha = Intercept$

 $\beta = slope$

X= Covariate i.e. Baseline of respective vital signs parameter The hypothesis is as follows

H0: $\beta = 0$

i.e. There is no statistically significant change in respective vital signs parameter at week 24 from baseline depending on the Baseline of respective vital signs parameter.

V/s

H1: β ≠ 0

i.e. There is statistically significant change in respective vital signs parameter at week 24 from baseline depending on the Baseline of respective vital signs parameter.

The above hypothesis will be tested based on α (alpha)=0.05, if the p-value \geq 0.05 then we will conclude that there is no statistically significant change in respective vital signs parameter at week 24 from baseline i.e. Ho is accepted.

The sample SAS programme is as follows:

proc mixed data=dataset;

model Y= X / s cl;

estimate "Model with Mean of baseline respective vital signs parameter " int 1 vital signs parameter baseline mean /CL;

ods output estimates=output dataset;

run; quit;

19. Primary efficacy assessments

The primary endpoint parameter is mention below

- 19.1 Variables and derivations
- 19.1.1 Incidence of total (symptomatic or asymptomatic with FBG level of ≤54 mg/dL [≤3.0 mmol/L]) hypoglycaemic events at Week 24

Variables:

- What was the blood glucose level (mg/dL) prior to treating the event? (In eCRF "Hypoglycemia Events" form)
- Were signs/symptoms of hypoglycemia present, other than the blood glucose reading? (In eCRF "Hypoglycemia Events" form)
- Hypoglycemic event start date
- Date of Visit 2 (Week 0)
- Date of Visit 8 (Week 24)

Derivation:

- Hypoglycemic event start date ≥ Date of Visit 2 (Week 0) and Hypoglycemic event start date ≤ Date of Visit 8 (Week 24) for accessing the hypoglycemic events from Day 0 to week 24.
- "Symptomatic Hypoglycaemic events" if, the question "What was the blood glucose level (mg/dL) prior to treating the event" result is less or equal to 54 mg/dL and the question "Were signs/symptoms of hypoglycemia present, other than the blood glucose reading" is answered as "YES".
- "Asymptomatic Hypoglycaemic events" if, the question "What was the blood glucose level (mg/dL) prior to treating the event" result is less or equal to 54 mg/dL and the question "Were signs/symptoms of hypoglycemia present, other than the blood glucose reading" is answered as "NO" or "UNKNOWN.

